4.13.2 Deaths, Serious Adverse Events, and Other Significant Adverse Events

Describe the listings that are to be provided. These may include the following listings:

• A by-patient listing of all SAEs

• A by-patient listing of all AES leading to discontinuation of study treatment

Listings should follow the format described for AEs in Section 4.13.1 if appropriate.

4.13.3 Clinical Laboratory Evaluation

Clinical laboratory test results of hematology, clinical chemistry, urinalysis, urinary drug screening, coagulation and serology will be provided by patient.

All TLFs will display only the standard international (SI) units after conversion by means of standard conversion factors.

Quantitative clinical laboratory variables, i.e., hematology, clinical chemistry, coagulation and urinalysis will be summarized using descriptive statistics (n, mean, SD, minimum, maximum and median) by cohort, treatment group and time-point. Additionally, a within-patient change will be calculated as the post-baseline measurement minus the baseline measurement and summarized in the same way.

Baseline definition is defined in section 4.2.4.

Any quantitative laboratory parameters that are given as '<xx' or '>xx' in the database will be imputed with the absolute value of the number without the sign (e.g., <2.2 will be imputed as 2.2) for the calculation of the changes from baseline and for the descriptive statistics. In the listings, no imputations will be performed, and all data will be displayed as recorded in the database.

Each laboratory result will be classified as low (L), normal (N), or high (H) at each time point according to the laboratory supplied reference ranges. For hematology, clinical chemistry, coagulation and urinalysis, shift tables will be presented showing the number and percentage of patients with shifts from baseline to each post dose time point. Tabulations will be presented by cohort and treatment group.

Measurements obtained at Screening will not be included in the shift tables and in the tabulations of descriptive statistics.

Measurements obtained prior to dosing in each period will be included in the tabulations for the treatment received in that specific treatment period.

Frequency tabulations of qualitative clinical laboratory variables (urinalysis) will be presented by cohort, treatment group and time-point.

All laboratory data will be displayed in listings.

Laboratory abnormalities that are considered clinically significant (CS) are recorded in the database as AEs. Therefore, no tabulation of laboratory values meeting any CS criteria (except liver chemistry) will be presented as all relevant information will be presented in the AE summaries.

Results of pregnancy tests (females only), viral serology, covid-19 test, urine drug screening, cotinine test, and alcohol tests will be listed in other laboratory test.

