5.2 Exclusion Criteria

Patients who meet one or more of the following criteria will not be considered eligible to participate in the clinical study:

1. Female patients who are breastfeeding or have a positive urine pregnancy test either at the Screening Visit or at Admission.
2. Patients who are unable to eat the prescribed meals during the stay at the site; vegetarian or vegan.
3. Patient has a history of significant drug allergy, as determined by the Investigator.
4. Patient has used a study drug, any prohibited medication(s) (see Section 6.8.2), over-the-counter (OTC) medications, vitamins, dietary and herbal supplements within 14 days or 5 half-lives if known (whichever is longer) prior to the first dose of study drug.
5. Patient has a history of active suicidal ideation in the past 6 months prior to the Screening Visit, or any psychiatric disorders that will affect the patient's ability to participate in the study as determined by the Investigator.
6. Patient has a current or recent (within 14 days prior to the Screening Visit) history of uncontrolled, clinically significant infectious, hematological, renal, endocrine, pulmonary, gastrointestinal, cardiovascular, hepatic, psychiatric, neurologic, or allergic disease.
7. Patient with any of the following laboratory abnormalities either at the Screening Visit or at Admission. These assessments may be repeated once at the discretion of the Investigator.
 - a. Aspartate aminotransferase (AST), alanine aminotransferase (ALT) \geq 2 times the upper limit of normal (ULN)
 - b. Bilirubin \geq 1.5 times ULN
 - c. An estimated glomerular filtration rate (eGFR) according to Cockcroft-Gault \leq 60 mL/min
 - d. Hematology values below the lower limit of normal: Neutropenia, absolute neutrophil count $<$ 1000/mm³, hemoglobin $<$ 9 g/dL, white blood cell $<$ 2.5 \times 10³/ μ L
 - e. Clinically significant abnormalities, as judged by the Investigator
8. Patient has a history of alcohol and/or drug abuse within 24 weeks of the Screening Visit.
9. Patient has positive results for drug testing either at the Screening Visit or at Admission.
10. Patient has positive breath alcohol test either at the Screening Visit or at Admission.

11. Regular consumption of alcohol within 6 months prior to the Screening Visit

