7.1.1 Overall Study Stopping Criteria

The study will be stopped if any of the following occur and are thought to be at least possibly related to study intervention agreed upon by the SRC:

- Two patients develop the same Grade 3 AE (grading is based on the Common Terminology Criteria for Adverse Events [CTCAE] version 5.0).
- One patient develops \geq Grade 4 AE (CTCAE version 5.0).
- Death of a patient at any time.

If any of the following scenarios occur within a cohort with reasonable possibility of a causal relationship with study drug, dosing will be stopped, and further dosing will not be initiated.

- One or more patients experience increased alanine ALT or AST $> 3 \times$ ULN with total bilirubin (TBL) $> 2 \times$ ULN or increased AST $> 3 \times$ ULN accompanied by alkaline phosphatase (ALP) $> 1.5 \times$ ULN.
- One or more patients experience a decrease of absolute neutrophil count less than 1,000/mm³ or white blood cell (WBC) less than $2.5 \times 10^3/\mu\text{L}$ or platelet count less than 75,000/ μL .
- One or more patients have an increase of more than 60 ms in QTcF compared to the baseline QTcF (baseline QTcF = value obtained on Day 1 at pre-dose in the treatment period) or QTcF > 500 ms or other clinically significant conduction disturbance or arrhythmia. All ECGs for this determination must be performed under strict resting conditions.
- Two or more patients, who receive study intervention, have tachycardia defined as resting supine heart rate > 125 beats per minute (bpm) persisting for at least 10 minutes.
- Two or more patients, who receive study intervention, have symptomatic bradycardia defined as resting supine heart rate < 40 bpm accompanied with symptoms of bradycardia while awake persisting for at least 10 minutes.
- Two or more patients, who receive study intervention, develop hypertension defined as an increase in resting supine systolic blood pressure (BP) > 40 mmHg to above a reading of 180 mmHg and persisting for at least 10 minutes.

If the criteria were met, the SRC will carefully review the totality of data, considering moderate non-serious AEs at least possibly related to the study intervention administration in unblinded

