8.4.6 Adverse events of Special Interest

An AESI (serious or non-serious) is one of scientific and medical concern specific to the Sponsor's product or program, for which ongoing monitoring and rapid communication by the Investigator to the Sponsor can be appropriate. Such an event might warrant further investigation to characterize and understand it. Depending on the nature of the event, rapid communication by the Sponsor to other parties might also be warranted.

AESIs are required to be reported by the Investigator to the Sponsor immediately (i.e., within 24 hours after learning of the event) regardless of their causality to the study treatment. The most appropriate diagnosis or if a diagnosis cannot be established, the abnormal laboratory values should be recorded on the eCRF and reported to the Sponsor immediately (i.e., within 24 hours after learning of the event), either as a SAE or an AESI. Based on CDK4/6 inhibition mechanism of action, the following AEs will be defined as AESIs:

- Myelosuppression: Hematology including monitoring for neutropenia, leucopenia, thrombocytopenia, and increased tendency to bleed
- Embryo-fetal toxicity: highly effective methods of contraception will be used by the patients until 21 days after receiving the study drug
- Interstitial lung disease: Pulmonary symptoms (dyspnea, pyrexia, and cough)
- Gastrointestinal toxicity: e.g., diarrhea, nausea, vomiting, and abdominal pain

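### Low/normal/high shift tables do not register worsening past the protocol's own laboratory limits from an out-of-range baseline, and no planned haematology table counts it

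*SAP*

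**What the plan says.** **Scale.** SAP 4.13.3 states: "Each laboratory result will be classified as low (L), normal (N), or high (H) at each time point", using the laboratory's reference ranges. From this, "shift tables will be presented showing the number and percentage of patients with shifts from baseline to each post dose time point". The same section says that values meeting clinical-significance criteria will not be tabulated, because such abnormalities are recorded as adverse events. It makes one exception, for liver chemistry, without criteria.

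**Entry.** Protocol 5.2, exclusion 7, removes patients with AST or ALT at or above 2 x ULN (7a) or bilirubin at or above 1.5 x ULN (7b). Item 7d opens "Hematology values below the lower limit of normal: Neutropenia, absolute neutrophil count" and then gives figures: neutrophils below 1,000/mm³, hemoglobin below 9 g/dL, WBC below 2.5 x 10³/µL. It gives no platelet figure. Item 7e adds "Clinically significant abnormalities, as judged by the Investigator".

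**Limits during the study.** Protocol 7.1.1 stops dosing in a cohort on several findings, among them "One or more patients experience a decrease of absolute neutrophil count less than 1,000/mm³", WBC below 2.5 x 10³/µL or platelets below 75,000/µL. Protocol 7.2 sets patient-level limits: the same neutrophil and WBC figures, hemoglobin below 9 g/dL, creatinine above 3 x ULN, bilirubin above 2 x ULN, and AST or ALT above 3 x ULN.

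**Role of the data.** The incidence of laboratory abnormalities is a primary endpoint (protocol Table 3-1, SAP 2.1). Protocol 8.4.6 lists as an event of special interest "Myelosuppression: Hematology including monitoring for neutropenia, leucopenia, thrombocytopenia, and increased tendency to bleed".

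**The concern.** A three-category scale has one category on each side of the range. A patient already in the low category cannot move lower, and a patient already in the high category cannot move higher, whatever the size of the change. The entry criteria allow some patients to start there. A patient who starts in range can move, but the table does not say how far.

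With six active patients per dose, the useful safety summary is a count of patients who passed a meaningful limit, set beside pooled placebo. The protocol names such limits for blood counts, liver tests and creatinine. The SAP takes this approach for the ECG, where 4.13.5 and 6.4 count patients by QTcF bands (450, 480 and 500 msec; increases of 30 and 60 msec). It plans nothing comparable for blood counts, although the drug's mechanism makes myelosuppression an event of special interest.

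**Working it through.** The plan gives no figure to reproduce: there is no hypothesis (protocol 9.1) and no sample size calculation (protocol 9.4). The check applies the SAP's classification rule to pairs of values.

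**Step 1. Can a baseline be out of range?** SAP 4.2.4 takes the last value before first dose, planned as the Day 1 pre-dose sample.
- AST/ALT and bilirubin: yes. Values between 1 and 2 x ULN, and between 1 and 1.5 x ULN, do not meet exclusions 7a and 7b.
- Blood counts: yes, if the figures in 7d are the operative limits. If the lead-in of 7d excludes every low value, a low baseline is still possible. Protocol 10.2 assigns Screening and Day -1 to local laboratories and Day 1 onward to the central laboratory, so the eligibility result and the baseline come from different samples and laboratories.

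**Step 2. What does the table show?** The documents give no reference limits, so the lower limits of normal (LLN) are assumptions. On the low side, the illustrative baseline is the midpoint of the protocol limit and the LLN, and the later value is 0.9 x the protocol limit. On the high side, the baseline is 0.95 x the entry limit and the later value is 1.1 x the 7.2 limit.

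| Analyte | Protocol limit | Assumed LLN | Baseline | Later value | Cell | Limit crossed |
|---|---|---|---|---|---|---|
| Neutrophils, /mm³ | 1,000 | 1,500 | 1,250 | 900 | L to L | yes |
| Neutrophils, /mm³ | 1,000 | 2,000 | 1,500 | 900 | L to L | yes |
| WBC, 10³/µL | 2.5 | 3.5 | 3.0 | 2.25 | L to L | yes |
| Hemoglobin, g/dL | 9 | 11.5 | 10.25 | 8.1 | L to L | yes |
| Platelets, 10³/µL | 75 | 130 | 102.5 | 67.5 | L to L | yes |
| ALT/AST, x ULN | 3 | – | 1.9 | 3.3 | H to H | yes |
| Bilirubin, x ULN | 2 | – | 1.425 | 2.2 | H to H | yes |

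The low-side result does not depend on the LLN chosen. If limit ≤ baseline < LLN and the later value is below the limit, both values are below the LLN and the cell is L to L. Raising the assumed LLN to 4.5 (WBC), 13.5 (hemoglobin) or 150 (platelets) changes nothing.

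**Step 3. Patients normal at baseline.** With an LLN of 1,500/mm³, take a baseline of 1.05 x 1,500 = 1,575. A fall to 0.98 x 1,500 = 1,470 is N to L. A fall to 900, past the 7.1.1 limit, is also N to L.

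**Step 4. Size.** An active group has 6 patients. One patient of the Step 2 kind gives 0/6 shifts where a count of crossings gives 1/6 = 16.7%. Two give 0/6 against 2/6 = 33.3%. How often this would happen is unknown. If the chance per patient were 5%, 10% or 20% (assumed), the chance of at least one among 6 would be 1 − (1 − p)⁶ = 26.5%, 46.9% or 73.8%.

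**Step 5. Does another planned output count these patients?** For liver tests, possibly: the exception in 4.13.3 implies a table with unstated criteria. For blood counts, the SAP plans descriptive statistics with minimum and change from baseline, listings, and adverse-event summaries. The first two do not give a number of patients past a limit. The third gives one only for events that the investigator reports.

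**The case against.** The best defence is that the SAP chose this route deliberately. Clinically significant abnormalities become adverse events and are counted there. Myelosuppression is reportable within 24 hours regardless of causality (protocol 8.4.6), and SAP 4.13.1 counts patients with events of special interest by number and percentage. Severity is summarized by CTCAE grade if it is reported that way, as protocol 10.3.3 requires. A patient who meets a 7.2 limit while on treatment would also appear among discontinuations. In a group of six, a large fall is easy to see in the minimum change and in a short listing. Protocol 9.3.2.4 promises shift tables for selected parameters and names no scale, so the SAP does not depart from it.

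Most of this stands, and it rules out some stronger readings that a reader might infer:
- That the plan is blind to myelosuppression, or that L/N/H shifts are its only categorical laboratory output. The special-interest summary, the liver exception and the qualitative urinalysis frequencies contradict this.
- That low blood counts are plainly admitted. The lead-in of 7d is ambiguous, and 7e gives the investigator a further ground for exclusion.
- That a known share of patients would go uncounted. The documents give no rate of out-of-range baselines.
- That dose escalation is affected. It rests on committee review of the data (protocol 7.1.2), not on the final shift tables.

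The defence does not supply an objective count. The adverse-event route depends on investigator judgement, and protocol 8.3.5 by default treats findings associated with the underlying disease as not clinically significant unless they are judged more severe than expected.

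**Conclusion.** The point holds as a modest reporting gap. The L/N/H shift tables cannot show worsening within the low or high category, and they do not separate trivial from limit-crossing falls in patients who start normal. The first part is certain for AST/ALT and bilirubin. For blood counts it depends on how 7d is read, or on the local and central laboratories differing. The second part needs no abnormal baseline.

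The information is not lost, but no planned haematology table counts patients past the protocol's limits by dose against pooled placebo, and laboratory abnormalities are a primary endpoint. Each uncounted patient is 16.7 percentage points of an active group. That figure rests only on the group size of six. The example values and reference limits are assumptions, and the conclusion needs only that each lower reference limit lies above the corresponding protocol limit.

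**What to change.** Keep the L/N/H shift tables for all analytes. For neutrophils, WBC, hemoglobin, platelets, ALT, AST, total bilirubin and creatinine, add one of the following, by cohort and pooled placebo:
- a shift from baseline to post-baseline CTCAE v5.0 grade, the scale that the protocol uses for adverse events; or
- the number and percentage of patients crossing each laboratory limit named in protocol 7.1.1 and 7.2.

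The second option uses only figures already in the protocol. In either case, state the criteria for the liver-chemistry exception in SAP 4.13.3.

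The cost is SAP wording, derived variables from data already collected, and slightly larger tables for eight analytes. SAP section 1 provides a modification form for changes after finalization. No clinical limit is changed.

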8.3.5 Clinical Safety Laboratory Tests

Refer to [Appendix 2](#) (Section 10.2) for the list of clinical laboratory tests to be performed and the SoA ([Table 1-1](#)) for the timing and frequency.

The Investigator must review the laboratory report, document this review, and record any clinically significant changes occurring during the study as an AE. The laboratory reports must be filed with the source documents.

Abnormal laboratory findings associated with the underlying disease are not considered clinically significant unless judged by the Investigator to be more severe than expected for the patient's condition.

All laboratory tests with values considered clinically abnormal during participation in the study or within 2 months after the last dose of study intervention should be repeated until the values return to normal or baseline or are no longer considered clinically significant by the Investigator or Medical Monitor.

- a. If clinically significant/any values do not return to normal/baseline within a period of time judged reasonable by the Investigator, the etiology should be identified, where possible, and the Sponsor notified.
- b. All protocol-required laboratory tests, as defined in [Appendix 2](#) (Section 10.2), must be conducted in accordance with the laboratory manual and the SoA ([Table 1-1](#)).
- c. If laboratory values from laboratory tests not specified in the protocol and performed at the institution's local laboratory result in the need for a change in patient management or are considered clinically relevant by the Investigator (e.g., are considered to be an SAE or an AE or require dose modification), then the results must be recorded.

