
Any clinically significant abnormal laboratory findings or other abnormal safety assessments that are associated with the underlying disease, unless judged by the Investigator to be more severe than expected for the patient's condition.
 
The disease/disorder being studied or expected progression, signs, or symptoms of the disease/disorder being studied, unless more severe than expected for the patient's condition.
 
Medical or surgical procedure (e.g., endoscopy, appendectomy): the condition that leads to the procedure is the AE.
 
Situations in which an untoward medical occurrence did not occur (social and/or convenience admission to a hospital).
 
Anticipated day-to-day fluctuations of pre-existing disease(s) or condition(s) present or detected at the start of the study that do not worsen.

AE=adverse event; ECG=electrocardiogram; SAE=serious adverse event.

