3.2 Endpoints and Associated Variables

3.2.1 Safety Variables

The following safety and tolerability variables will be recorded at regular intervals during the study:

- Vital signs (supine blood pressure [BP] and pulse rate, tympanic (ear) body temperature, respiratory rate)
- Cardiac safety for arrythmias, abnormalities including PR interval, QRS interval, RR interval, QT interval, and QT interval corrected for heart rate (QTc) (Fridericia's correction [QTcF]) as assessed by 12-lead electrocardiogram (ECG) and cardiac telemetry.
- Incidence of laboratory abnormalities: hematology, clinical chemistry, coagulation, and urinalysis
- Incidence and severity of adverse event (AE) and adverse event of special interest (AESI) (i.e., gastrointestinal toxicity and pulmonary symptoms indicative of interstitial lung disease) assessments
- Physical examinations

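### The SAP reports laboratory abnormalities visit by visit but never per patient over the study, and its reason for omitting a table of clinically significant values conflicts with the protocol's AE definition

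*SAP*

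**What the plan says.** Both documents name this component in the primary endpoint. SAP 3.2.1 lists "Incidence of laboratory abnormalities: hematology, clinical chemistry, coagulation, and urinalysis".

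SAP 4.13.3 sets out the analysis:

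- "Each laboratory result will be classified as low (L), normal (N), or high (H) at each time point", using the laboratory's reference ranges.
- For all four panels, "shift tables will be presented showing the number and percentage of patients with shifts from baseline to each post dose time point", by cohort and treatment group.
- Descriptive statistics (including minimum and maximum) by time point, frequency tables for qualitative urinalysis, and listings of all data.
- No table of clinically significant (CS) values. The stated premise is "Laboratory abnormalities that are considered clinically significant (CS) are recorded in the database as AEs", and the consequence drawn is "Therefore, no tabulation of laboratory values meeting any CS criteria (except liver chemistry) will be presented". No criteria are given for the liver exception.

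The protocol says two different things about findings linked to rheumatoid arthritis (RA). Section 10.3.1, under events that do not meet the AE definition, lists "Any clinically significant abnormal laboratory findings or other abnormal safety assessments that are associated with the underlying disease, unless judged by the Investigator" to be worse than expected. Section 8.3.5 requires CS changes to be recorded as AEs, but adds: "Abnormal laboratory findings associated with the underlying disease are not considered clinically significant unless judged by the Investigator to be more severe" than expected.

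SAP 4.2.5 leaves repeat, retest and unscheduled assessments out of summary statistics and figures unless they serve as baseline.

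**The concern.** An incidence is normally a count of patients who had the event at least once. None of the planned laboratory tables gives that count. The SAP also rules out the one table that might have come close, and the premise it gives is not one the protocol consistently supports.

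The protocol sets numeric laboratory limits of its own. Among the triggers for stopping dosing, section 7.1.1 has "One or more patients experience a decrease of absolute neutrophil count less than 1,000/mm" (cubed in the source), followed by WBC below 2.5 × 10³/µL and platelets below 75,000/µL. Section 7.2 adds hemoglobin below 9 g/dL, along with creatinine and liver limits. Myelosuppression is the first AE of special interest listed for this CDK4/6 inhibitor. Yet no table will show, by dose and against placebo, how many patients crossed those limits. By contrast, SAP 4.13.5 and 6.4 do count patients by QT and QTcF threshold.

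**Working it through.** The plan states no figure for this point, so there is nothing to reproduce. The check has three parts.

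**1. What by-visit counts can tell.** Scheduled post-dose laboratory days, from protocol Table 1-1 and its footnote 4, are Days 4, 7, 8, 9, 10 and 14, which makes 6. Day 1 is drawn before dosing. Each active arm has n = 6.

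For one parameter, let c_v be the number of patients abnormal at visit v. The number ever abnormal at a scheduled visit lies between max(c_v) and min(n, Σc_v). Two illustrations with assumed data:

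| Counts on Days 4, 7, 8, 9, 10, 14 | Lower bound | Upper bound |
|---|---|---|
| 1, 1, 1, 0, 0, 0 | 1/6 = 16.7% | min(6, 3)/6 = 3/6 = 50% |
| 1, 1, 1, 1, 1, 1 | 1/6 = 16.7% | min(6, 6)/6 = 6/6 = 100% |

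In the first row, if three different patients are each low once, the true incidence is 50%, while no shift table shows more than 16.7%. Abnormal values seen only on repeat or unscheduled draws could raise the true figure above these bounds. Protocol 8.3.5 requires clinically abnormal values to be repeated, so such draws are expected.

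**2. What low/normal/high can tell.** A neutrophil count of 900/mm³ and one just under the reference limit are both classed as low. Suppose the laboratory's lower limit for hemoglobin is above 9 g/dL (an assumption, since ranges are not given). A patient who enters low but not below 9 g/dL, the numeric exclusion value in protocol 5.2, and then falls below 9 g/dL appears as low-to-low, with no shift.

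**3. Where a finding attributed to RA, and judged no worse than expected, goes.**

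| Text | Clinically significant? | AE under that text? | In a CS table? |
|---|---|---|---|
| SAP 4.13.3 premise | If yes | Yes | No (liver excepted) |
| Protocol 10.3.1 | Can be | No | No (liver excepted) |
| Protocol 8.3.5 | No | Not required | No |

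Section 10.3.1 contradicts the SAP's premise. Section 8.3.5 is formally consistent with it, but only because it removes the CS label. Under either protocol section the general AE rule does not bring the finding into the AE summaries, so the SAP cannot rely on those summaries to stand in for the omitted table.

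**The case against.** A reader might infer that the primary endpoint component is not produced at all, that a fall attributed to RA reaches no table, or that the reported incidence depends on the investigator's attribution. The documents do not support any of these.

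- The shift tables give number and percentage of patients for all four panels. This is more than protocol 9.3.2.4, which promises shift tables only for selected parameters. The classification rests on the reference range, so an out-of-range value at a scheduled visit is tabulated whatever its cause.
- The by-visit minimum would print a neutrophil count of 900/mm³ drawn at a scheduled visit, and with 32 patients the listings can be counted by hand.
- Neutropenia, leucopenia and thrombocytopenia are AEs of special interest. Protocol 8.4.6 requires them to be reported regardless of causality to study treatment, and SAP 4.13.1 tabulates them by SOC and PT.
- Patients crossing the limits in protocol 7.2 leave further dosing, and SAP 4.4.2 tabulates withdrawals with reasons.
- Protocol 8.3.5 agrees with the SAP's premise, so the protocol is inconsistent with itself rather than simply opposed to the SAP.

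All of this stands, and it narrows the point. It does not close it. The special-interest route has no numeric threshold and does not name hemoglobin. The withdrawal reasons in protocol 7.2 are broad categories, not laboratory limits. A minimum shows the worst value but not how many patients crossed a limit. Listings are not a planned incidence analysis.

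**Conclusion.** The point holds in this form: the plan gives per-visit incidence of out-of-range values, but no any-time incidence per patient and no count against the protocol's own laboratory limits. Its reason for omitting a CS table rests on a premise that protocol 10.3.1 contradicts and that protocol 8.3.5 supports only by relabelling.

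The size is limited. The study is descriptive, with no hypotheses and a sample size set by feasibility, so no test or power figure is affected, and every value is listed. For a single parameter in an arm of six, the by-visit counts can leave the any-time incidence undetermined between 16.7% and 100%. That range comes from an assumed pattern and is not a forecast. The change is worth making because this is a primary endpoint component and hematology is a stated safety interest. The conclusion assumes that SAP 4.2.5 applies to the shift-table counts, which is its natural reading.

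**What to change.** 1. In SAP 4.13.3, delete the sentence that rules out the table. If a separate liver table is kept, state its criteria.
2. Add one table by dose cohort and pooled placebo: number and percentage of patients by worst post-baseline CTCAE v5.0 grade for the hematology and chemistry parameters that can be graded, with baseline grade shown. Protocol 10.3.3 already uses this scale.
3. In that table, add rows for patients who ever met each laboratory limit exactly as printed in protocol 7.1.1 and 7.2. These rows count measured values, not causality judgements or stopping decisions.
4. Use all post-baseline values regardless of AE or CS status, and write an explicit exception to SAP 4.2.5 so that repeat and unscheduled values count.
5. If wanted, add a second table of patients ever low or high for coagulation and urinalysis, which the endpoint also names.
6. Reconcile protocol 8.3.5 with 10.3.1 on whether a finding linked to RA can be clinically significant.

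The cost is SAP wording, one or two tables programmed from data already collected, and a protocol clarification. If the SAP is already final, the analysis change belongs in the modification form that SAP section 1 provides for.
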